16.5 A. How long will the data be stored?

Response:

Hard copies will be destroyed after two years of the study period. The SPSS data will be stored for 10 years for publication.

16.6 A. Who will have access to the data?

Response:

The study OTGS who collect data and the PI.

16.7 A. Who is responsible for receipt or transmission of the data?

Response:

The study OTGS who collect data and the PI.

16.8 A. How will the data be transported?

Response:

A person who collect data will transfer the data form hard copy to a SPSS database in the SPHHP computer lab and store the data in the UB BOX. Another person who verify access the file in the UB Box.

B. Confidentiality of Study Specimens

*Describe the local procedures for maintenance of confidentiality of **study specimens**.*

N/A: No specimens will be collected or analyzed in this research.
(Skip to Section 19.0) **Does this mean Section 17.0?**

16.9 B. Where and how will all specimens be stored? Include information about: physical controls, authorization of access, and labeling of specimens, as applicable.

Response:

16.10 B. How long will the specimens be stored?

Response:

16.11 B. Who will have access to the specimens?

Response:

16.12 B. Who is responsible for receipt or transmission of the specimens?

Response:

16.13 B. How will the specimens be transported?

Response:

17.0 Provisions to Monitor the Data to Ensure the Safety of Subjects

- N/A: This study is not enrolling subjects, or is limited to records review procedures only. This section does not apply.

NOTE: *Minimal risk studies may be required to monitor subject safety if the research procedures include procedures that present unique risks to subjects that require monitoring. Some examples include: exercising to exertion, or instruments that elicit suicidality or substance abuse behavior. In such cases, N/A is not an acceptable response.*

17.1 Describe the plan to periodically evaluate the data collected regarding both harms and benefits to determine whether subjects remain safe.

Response:

We will not periodically evaluate the data collected but we will collect data every 2 months for three times. The study will identify depression. If the total score of CES-D is 15 or higher at the time of interview, this will be reported to the participant and the PACE for an appropriate intervention.

17.2 Describe what data are reviewed, including safety data, untoward events, and efficacy data.

Response:

The total score of the Center for Epidemiology Study-Depression will be used to detect depression, which is a considered mental illness.

17.3 Describe any safety endpoints.

Response:

The CES-D total score of 14 or less (not depressive) and 15 or higher (indicative of depressive symptom). One of the purpose of the study is to decrease the CES-D score.

17.4 Describe how the safety information will be collected (e.g., with case report forms, at study visits, by telephone calls with participants).

Response:

Face-to face interviews.

17.5 Describe the frequency of safety data collection.

Response:

Three times in 4 months.

17.6 Describe who will review the safety data.

Response:

Study OTGS and the PI

17.7 Describe the frequency or periodicity of review of cumulative safety data.

Response:

We do not have cumulative safety data. When each time we interview participants, we will review the data.

17.8 Describe the statistical tests for analyzing the safety data to determine whether harm is occurring.

Response:

The sum of 20 item CES-D scores will be used.

17.9 Describe any conditions that trigger an immediate suspension of the research.

Response:

If the CES-D score is 15 or higher, it will be reported to the PACE for possible intervention, in accordance with their policy. We do not have any conditions that will be used for immediate suspension of the participant form our research.

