1.0 Objectives

1.1 Describe the purpose, specific aims, or objectives of this research.

Response:

The purpose of this project is to develop and test affordable, effective strategies to reduce caregiver burden and associated negative effects (e.g., depression and fatigue) and to increase caregivers' satisfaction and self-efficacy, so that they can continue providing home-based care to their care recipients (CRs) who are members of the Program of All-inclusive Care for the Elderly (PACE). This project will connect PACE organizations and university occupational therapy (OT) graduate level curriculum to produce a practical, sustainable care model. In this project, a research component pertains to assess effectiveness of OT interventions

1.2 State the hypotheses to be tested, if applicable.

NOTE: A hypothesis is a specific, testable prediction about what you expect to happen in your study that corresponds with your above listed objectives.

Response:

We have three reteach questions and two hypotheses.

1. What are challenges that caregivers are facing in caring for their care recipients?
2. Which solutions were accepted and effective?
3. The intervention group will reduce caregiver burden and depression, while the control group will not.
4. The intervention group will increase the scores of positive aspect of caregiving and self-efficacy while the control group will not.
5. At 6-months after intervention, does the effect of our intervention exist?

In addition, we will identify the rate of care recipients who live in the community opposed to moving to a nursing home for both groups, and the number of falls and emerveny visits of care recipients.

Scientific Endpoints

2.1 Describe the scientific endpoint(s), the main result or occurrence under study.

*NOTE: Scientific endpoints are outcomes defined before the study begins to determine whether the objectives of the study have been met and to draw conclusions from the data. Include primary and secondary endpoints. Some example endpoints are: reduction of symptoms, improvement in quality of life, or survival. Your response should **not** be a date.*

Response:

Primary endpoint for the study is the reduction of caregiver burden and depression. Secondary endpoints is the improvement in positive aspect of caregiving and self-esteem.

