9.0 Procedures Involved

9.1 Provide a description of **all research procedures or activities being performed and when they are performed once a subject is screened and determined to be eligible. Provide as much detail as possible.**

NOTE: This should serve as a blueprint for your study and include enough detail so that another investigator could pick up your protocol and replicate the research. For studies that have multiple or complex visits or procedures, consider the addition of a schedule of events table in in your response.

Response:

After obtaining approval from the IRB, UB OT graduate students (OTGS) will be educated and trained for 2 months prior to the start of the intervention. They will study the protocol, interview methods, and interventions. PACE rehabilitation, department staff will also be educated

about the protocol and they will mail an invitation letter and a flyer to caregivers of person with dementia. These records are readily available at the PACE as a standard record keeping procedure.

Interested caregivers will contact the PI and will be screened for eligibility for the study.

OTGS will make an appointment to visit participants. While reading a consent form, an OTGS will explain the study in detail and make sure that the caregiver understand the content. Their right to withdraw from the study without penalty will be explained. After obtaining written consent, a structured interview will take place about 30 minutes. It starts with asking demographic questions, care recipient's cognitive and physical function, levels of assistance the caregiver is providing, and followed by questions about caregivers. This section will ask caregiver burden, fatigue, depression, positive aspect of caregiving, and self-efficacy in caregiving.

The OTGS will talk with caregivers to understand problems in depth. Examples may include difficulty in (a) understanding the disease development process and its consequences; (b) assisting care recipient (CR)'s ADL, IADL, and communication; (c) coping with CRs' undesirable behaviors (e.g., non-use of a stair glide, pulling a cord to turn off lights, reluctance in changing clothes and washing hair, inactivity and lack of motivation in daily routine); (d) maintaining caregivers' health and strength; (e) coordination of care among family members, and (f) having own time. In addition, we will specifically address fall prevention because PACE enrollees have a high fall rate.

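### The only safety endpoint, an absolute CES-D of 15 or more, can already be met at baseline, and the safety plan relates it neither to baseline nor to arm

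*Combined protocol and SAP*

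**What the plan says.** All references are to the combined protocol and SAP.

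- **Endpoint (17.3).** "The CES-D total score of 14 or less (not depressive) and 15 or higher (indicative of depressive symptom". No other safety endpoint is listed.
- **Test for harm (17.8).** The form asks which tests will determine whether harm is occurring. The whole answer is "The sum of 20 item CES-D scores will be used".
- **Review (17.1, 17.6, 17.7).** "We will not periodically evaluate the data collected but we will collect data every 2 months for three times". Section 17.7 says "We do not have cumulative safety data", but adds that the data are looked at whenever a participant is interviewed. Section 17.6 names the student interviewers and the PI as reviewers.
- **Schedule and mode (17.4, 17.5).** Face-to-face interviews, "Three times in 4 months".
- **Action (9.6, 17.1, 17.9, 19.2).** A score at or above the cut-off is reported to the participant and to the PACE. Section 17.9 adds "We do not have any conditions that will be used for immediate suspension of the participant form our research".
- **Baseline measurement (9.1).** Of the first structured interview: "This section will ask caregiver burden, fatigue, depression, positive aspect of caregiving, and self-efficacy in caregiving". The criteria in 5.1 and 5.2 do not mention CES-D.
- **Efficacy use (1.2, 2.1, 9.2, 16.1).** Depression, measured by CES-D, is a primary endpoint. The hypothesis reads "The intervention group will reduce caregiver burden and depression, while the control group will not". Section 16.1 compares the groups' slopes by GEE if the trend is linear, and otherwise uses repeated-measures ANOVA with a between-group factor. Within-group and between-group contrasts follow.

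**The concern.** A harm endpoint has to separate what was present at entry from what arose during the trial. A fixed cut-off on the current score does not. The trial recruits caregivers facing challenges and aims to lower their CES-D, so some can be expected to start at 15 or more. They meet the endpoint at the first interview and keep meeting it while they stay above the line, whether they improve or deteriorate.

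If depression arose or deepened in one arm, section 17 as written would lead to individual reports but to no summary showing it. A reader of the final results could not tell how many caregivers became depressed after entry, or in which arm.

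**Working it through.** **1. The plan's own figure.** The safety rule carries no statistical figure. The only design figure that can be reproduced is the sample size in 4.3 and 16.2 (d = 0.65, directional alpha 0.05, power 80%):

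n per group = 2 × (1.645 + 0.842)² / 0.65² = 12.37 / 0.4225 = 29.3, rounded up to 30.

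This matches the stated 30 per group. A two-sided 0.05 would give 2 × (1.960 + 0.842)² / 0.4225 = 37.2, rounded up to 38, so the size was set one-sided.

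**2. What the cut-off can and cannot distinguish.** Hypothetical scores, classified by 17.3:

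| Baseline | Later | Change | Class at baseline | Class later |
|---|---|---|---|---|
| 30 | 16 | −14 | 15 or more | 15 or more |
| 16 | 30 | +14 | 15 or more | 15 or more |
| 2 | 14 | +12 | 14 or less | 14 or less |
| 14 | 15 | +1 | 14 or less | 15 or more |

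The first two rows move in opposite directions and are classified alike. The third is a large rise that is never flagged. Only the fourth is new onset. Section 17 does not separate it from the first two, because it does not set the later score against the first.

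**3. How many could meet the endpoint before any intervention.** The documents give no baseline rate of CES-D at 15 or more, so a range p is assumed. Expected number among 60 = 60p:

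- p = 10%: 6
- p = 20%: 12
- p = 30%: 18
- p = 40%: 24
- p = 50%: 30

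The chance of at least one is 1 − (1 − p)^60. At p = 10% that is 1 − 0.9^60 = 0.998, and it is higher for larger p. The 60 is the enrolment number in 4.1. If all 75 mentioned in 16.2 were interviewed at baseline, the range would be 7.5 to 37.5.

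**4. Whether 16.1 fills the gap.** It compares CES-D over time and between groups, so average worsening in the treated arm could show there. It does not show individuals. Taking the first and fourth rows above together, the mean change is (−14 + 1) / 2 = −6.5, an average improvement in which one of two caregivers newly crosses 15. Section 17 does not refer to 16.1, and 16.1 does not mention safety.

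**5. What a by-arm comparison could deliver.** With 30 per arm and two-sided 0.05, power to detect harm of size d on the score is Φ(d√15 − 1.960):

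- d = 0.30: Φ(−0.798) = 21%
- d = 0.50: Φ(−0.023) = 49%
- d = 0.65: Φ(0.557) = 71%

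On the proportion at 15 or more (control rate assumed 20% to 40%, normal shift of size d), power is about 13–15%, 30–33% and 46–51%.

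For onset, those at risk per arm number 30(1 − p), that is 27 to 15. With no onsets seen, the upper limit of the exact 95% interval in an arm is 1 − 0.025^(1/27) = 12.8% to 1 − 0.025^(1/15) = 21.8%.

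**The case against.** Three points on the other side carry weight.

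**CES-D is compared elsewhere.** A reader might infer that CES-D is never compared with baseline or between arms. The documents do not support that, because 16.1 makes both comparisons for a primary endpoint. The gap is confined to the safety plan.

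**The efficacy analysis is not blind to harm.** A reader might argue that it is, because the hypothesis is directional. If the test were run one-sided towards benefit, it would reject with probability Φ(−0.30√15 − 1.645) = Φ(−2.807) = 0.25% under true harm of d = 0.30. But the directional statement stands in the sample-size text (4.3, 16.2). Section 16.1 gives only a .05 level and no sidedness, an ANOVA F test has no direction, and slopes and contrasts carry a sign. Average worsening could be seen. What stays hidden is individual worsening within a mean.

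**The cut-off serves another purpose.** It triggers a report to the participant and the PACE, and for that it is right that it can fire at baseline. No section says that scores of 15 or more will be counted as harm events by arm, so one cannot say that the trial will report a misleading count. Nor is there no review at all, since 17.6 and 17.7 provide for a look at each interview.

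What remains is that the plan calls this trigger its safety endpoint and offers the sum score as its answer on detecting harm. Low power also limits any remedy: a table from a trial of this size describes and does not settle the question.

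**Conclusion.** The concern holds for the safety plan. The endpoint in 17.3 can be met before any intervention, and 17.7 and 17.8 relate it neither to baseline nor to arm. It works for individual reporting, but it cannot show new or worsened depression. The comparison in 16.1 partly covers average worsening, is not linked to safety, and can conceal caregivers who newly cross 15.

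The logical part rests on the documents alone. The size, 6 to 30 of 60 at or above the cut-off at baseline, rests on an assumed rate of 10% to 50%. The severity is minor: a cheap improvement to the description of harms that does not threaten the primary analysis.

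**What to change.** Leave the reporting trigger at 15 as it stands, and change the analysis wording.

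- **17.3.** Define the safety endpoint for analysis as onset after baseline: 14 or less at baseline and 15 or more later. Also summarise change in CES-D from baseline for all participants, whatever their starting score. This makes visible both rises that stay below 15 and rises among those who start at 15 or more, without choosing a size of rise.
- **17.8.** State one descriptive table at the end of the study, by arm and post-baseline assessment, with exact 95% intervals for the difference in onset. Cross-refer to the CES-D comparison in 16.1 and say that it will be read in both directions.
- **17.7.** Keep the individual review at each interview, and say that the by-arm table is made only at the end. A running by-arm table for the PI would give unblinded interim looks at a primary outcome to the person supervising the student interviewers.
- **17.4 and 17.5.** If the final assessment is included, reconcile these with 9.1 and 11.1. They now cover only face-to-face interviews over 4 months, whereas the final assessment is by phone, 6 months after the intervention.

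The cost is some wording and one table from data already planned, with no new measurement. The counts will be small, so the table cannot rule out harm, and the text should say so.

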18.0 Withdrawal of Subjects

 N/A: This study is not enrolling subjects. This section does not apply.

18.1 Describe anticipated circumstances under which subjects may be withdrawn from the research without their consent.

Response:

We will not withdraw a participant from the research without their consent.

18.2 Describe any procedures for orderly termination.

NOTE: Examples may include return of study drug, exit interview with clinician. Include whether additional follow up is recommended for safety reasons for physical or emotional health.

Response:

If a participant decide to withdraw for the study, he/she will indicate it to an OTGS at the interview and the PI will confirm the wish through a phone contact with the participant.

18.3 Describe procedures that will be followed when subjects withdraw from the research, including retention of already collected data, and partial withdrawal from procedures with continued data collection, as applicable.

Response:

After the orderly termination, the data that had been collected until the withdrawal will be retained and analyzed. This information is included in the informed consent.

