16.0 Data Management and Analysis

16.1 *Describe the data analysis plan, including any statistical procedures. This section applies to both quantitative and qualitative analysis.*

Response:

For two hypotheses, we first analyze a linear trend of dependent variables over time. If they are linear, we will use Generalized Estimating Equation to compare the two groups' slopes. A main effect and an interaction effect will be examined. If it is not, we will use Repeated Measures ANOVA with a between-factor. The contrasts within a group and the difference between groups will be performed as post hoc tests. To answer the last research question to find the difference between

the 4-months data and 6 month after intervention (or at 10 months), we will use Repaeated measurs ANVA with a between-factor.

To answer research questions, we will list all challenges for both groups and solutions for the treatment group. The effectiveness of solutions will be evaluated using a Likert Scale (from very effective to not effective at all) and percentages will be reported. For the rate of continued community, living at 4 months will be tabulated for both groups and a chi-square test will be used. The number of falls and emergency visits will be compared for these two groups using Mann Whitney U-test.

The significance level for primary analyses will be set at .05. SPSS 26.0 will be used for statistical analyses.

16.2 If applicable, provide a power analysis.

NOTE: This may not apply to certain types of studies, including chart/records reviews, survey studies, or observational studies. This question is asked to elicit whether the investigator has an adequate sample size to achieve the study objectives and justify a conclusion.

Response:

The sample size for this study was determined by a power analysis based on the study similar to our study (Kamiya et al., 2014). The effect size found in the article was $d = .65$. We will use a directional hypothesis; therefore, we set $\alpha = .05$, and in order to achieve 80% of statistical power, we will need 30 participants in each group, therefore 60 in total. Expecting 25% of attrition, we will recruit 75 participants.

16.3 Describe any procedures that will be used for quality control of collected data.

Response:

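### Repeated measures ANOVA in 16.1, as normally run, would leave out withdrawn caregivers whose data 18.3 says will be analysed; the lost information is certain, bias only conditional

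*Combined protocol and SAP*

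**What the plan says.** Section 18.3 (Withdrawal of Subjects) states that after a caregiver withdraws "the data that had been collected until the withdrawal will be retained and analyzed", and adds that the consent form says so.

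Section 16.1 (Data Management and Analysis) has two routes for hypotheses 3 and 4:
- Linear trend: "If they are linear, we will use Generalized Estimating Equation to compare the two groups' slopes".
- Otherwise: "If it is not, we will use Repeated Measures ANOVA with a between-factor".

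Question 5 in section 1.2 asks: "At 6-months after intervention, does the effect of our intervention exist". For it, 16.1 gives one method and no alternative, comparing "the 4-months data and 6 month after intervention (or at 10 months), we will use Repaeated measurs ANVA with a between-factor".

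The software is fixed: "SPSS 26.0 will be used for statistical analyses". Section 16.2 anticipates substantial loss: "Expecting 25% of attrition, we will recruit 75 participants".

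No section defines an analysis set, a rule for missing visits or a sensitivity analysis. Missing data appear only in 16.3, as a data-entry check. Section 19.2 reports a CES-D total of 15 or more to PACE and says that the study will follow a PACE decision that the caregiver be withdrawn. Depression is one of the two primary endpoints.

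**The concern.** Standard repeated measures ANOVA needs a score at every visit entered in the model. A caregiver seen at month 4 but not reached for the 10-month call is removed from question 5, month-4 score included. On the non-linear branch, a caregiver seen at baseline and month 2 but not month 4 is removed from a 0/2/4-month test. Those tests then compare completers rather than the caregivers who were randomised, and they do not use data that 18.3 says will be analysed.

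If loss is unrelated to scores, or works the same way at the same rate in both arms, the price is information only. If loss depends on scores and differs between arms, the completers are no longer comparable and a group difference can appear where none exists. Section 19.2 makes dependence on a primary outcome plausible, because withdrawal may follow a high CES-D score. A difference between arms is also possible: only the treatment arm has the solution planning, and its contact with the study team is more intensive.

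**Working it through.** **The plan's own figure.** Inputs from 16.2: d = 0.65, directional α = 0.05, power 80%. Per group, n = 2(1.645 + 0.842)² / 0.65² = 12.37 / 0.4225 = 29.3, rounded up to 30. The exact noncentral-t power at 30 per group is 80.0%. The stated 30 per group is reproduced.

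**Caregivers affected.** 0.25 × 75 = 18.75, about 19, leaving 75 − 18.75 = 56.25, about 56. This is an upper figure for question 5, since 25% is attrition over the whole study. If 60 is the number enrolled, as section 4.1 says, it is 0.25 × 60 = 15. A 0/2/4-month test loses as many only if every loss comes before month 4, which the documents do not say.

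**Assumptions for the simulations.** The documents give no dropout mechanism and no correlation between visits, so these are assumed: no true effect, normal scores with SD 1, correlation 0.6, 37 per arm, 25% loss per arm, two-sided tests at 5%. Slopes are logistic, per SD of the score that drives loss.

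**Hypotheses 3 and 4, non-linear branch only.** This is the 0/2/4-month group-by-time ANOVA, with loss after month 2.

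| Assumed loss | Rejection rate |
|---|---|
| Random in both arms | 5.1% |
| Slope 1.5 on month-2 change, both arms | 5.1% |
| Slope 0.5, treated arm only | 6.2% |
| Slope 0.75, treated arm only | 8.0% |
| Slope 1.5, treated arm only | 13.8% (repeat runs 13.6% and 14.0%) |

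In the last row, the completer differences in change from baseline were −0.247, −0.120 and −0.122 SD at months 2, 4 and 10. A mixed model on all available scores gave −0.010, −0.005 and −0.002 SD (Monte Carlo standard error about 0.008).

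**Question 5, same month-2 mechanism.** With two visits, the group-by-time test is a t-test on the 4-to-10-month change. The bias is −0.122 − (−0.120) = −0.002 SD. Rejection was 5.0% for group-by-time and 5.2% for group, so there is no inflation. The −0.12 SD differences in change reflect a baseline imbalance of about 0.12 SD among completers, and question 5 does not use baseline.

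**Question 5, loss after month 4 driven by the month-4 score.** At correlation 0.6, mechanisms that differ by arm gave about 7% to 10% for group-by-time and 11% to 31% for the group effect. The dependence on the assumptions is shown by a separate set of runs (38 and 37 per arm, 6,000 runs each; correlation 0.5 / 0.7):

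| Assumed loss | Group-by-time | Group effect |
|---|---|---|
| Random | 5.1% / 5.1% | 4.9% / 4.5% |
| Slope 1, both arms | 4.8% / 5.0% | 4.8% / 4.7% |
| Slope 1, one arm | 6.9% / 5.9% | 10.7% / 11.1% |
| Slope 2, one arm | 9.5% / 7.3% | 17.9% / 20.7% |
| Opposite slopes of 1 | 13.2% / 9.5% | 28.8% / 33.7% |
| Opposite slopes of 2 | 22.3% / 14.7% | 61.3% / 69.1% |

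Group-by-time bias ran from 0 to 0.32 SD. A likelihood estimate that kept the month-4 scores of caregivers lost later had bias of at most about 0.006 SD.

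**The case against.** **No outright contradiction.** A reader might infer that 16.1 breaks a commitment made to participants. The documents do not support that. Section 18.3 answers a template question about keeping data; it does not say that the data enter every test. Section 16.1 never specifies complete cases; that follows from how the procedure is normally run and from the absence of a rule. Withdrawn caregivers' data can still enter GEE and the listings of challenges and solutions. This objection stands against the word contradiction. It does not remove the exclusion from the ANOVA tests.

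**The figure of about 14% is not a question 5 result.** A reader might take it as showing a false effect there. It belongs to the non-linear branch, and the same mechanism leaves question 5 at about 5%. This stands.

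**Some omissions come from the question, not the method.** A caregiver who leaves after month 2 has neither score that question 5 compares. Using that caregiver's earlier data means fitting a model to all visits, which is more than a change of method name. This also stands, and the fix is worded accordingly.

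**The mixed model's small bias is built in.** In these simulations loss depends only on observed scores, which is the missing-at-random condition. The runs do not show protection if loss depends on unobserved scores.

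**The 19.2 route is uncertain.** Section 18.1 says that nobody is withdrawn without consent, while 19.2 defers to PACE. The two need reconciling, and how often this route would operate is unknown.

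**Conclusion.** The point holds in a limited form. The repeated measures ANOVA tests in 16.1, as normally run in SPSS, would not use the data of caregivers missing an entered visit. That affects question 5 in every case, and hypotheses 3 and 4 only if the trend is not linear. On the linear branch GEE keeps earlier visits, although unweighted GEE generally needs loss unrelated to outcomes.

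Up to about 19 of 75 recruited caregivers would be excluded from question 5. That loss of information follows from the plan's own attrition figure. Inflated false positives do not: they need loss that depends on scores and differs by arm. Under the assumptions at correlation 0.6, the range is about 5% to 14% for the 0/2/4-month test. For question 5, with loss driven by the month-4 score and differing by arm, it is about 7% to 10% for group-by-time and 11% to 31% for group. These figures show how sensitive the method is; they do not predict this trial's error rate. The change should be made because it is cheap and brings the analysis into line with 18.3.

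**What to change.** In 16.1, replace both uses of repeated measures ANOVA with a likelihood-based mixed model for repeated measures (SPSS MIXED), with group, visit and group-by-visit terms. Fit it to all visits (baseline, 2, 4 and 10 months) for every randomised caregiver with a baseline score, in the assigned arm, using all scores up to withdrawal. Test question 5 as the 4-versus-10-month contrast between groups within that model. State that the model assumes data are missing at random, and report withdrawals by arm and last visit so that readers can judge that assumption.

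The cost is analysis wording only, plus open reliance on missing at random. The named software can fit the model, and no extra visits, data or caregivers are needed.
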